### 3.2.4 Functional Activity by Direct Skin Feeds

Direct skin feeds (DSF) were also used to assess vaccine activity. During the rainy season in 2017 (Year 1, Main Phase) and 2018 (Year 2, fourth dose), a total of 4861 DSFs were performed in 2017 and another 5056 DSFs were completed in 2018. There was a total of 40 positive DSFs (0.82%) from 19 unique individuals in 2017; and a total of 88 positive DSFs (1.74%) from 25 unique individuals in 2018 ([Table 6](#)). A trend of lower infections in the full dose regimen was observed in 2017 but not significant. Positive DSFs were significantly less frequent in the full dose regimen in 2018, a first and an extremely important achievement in the field of malaria transmission blocking vaccines – in vivo functional activity.

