**Table 7. Summary of Study Progress for 19-I-N086**

	Pilot Phase		Main Phase			
	Arm 2a/2b 5-8 yo	Arm 1a/1b 9-18 yo	Arm 3a/3b 5-8 yo	Arm 3c/3d 9-18 yo	Arm 3e/3f ≥19 yo	Arm 4a/4b 1-4 yo
Number subjects enrolled	30	30	185	369	495	192
Timing of enrollment	May 2019	Apr 2019	Jun to Sep 2019			Aug to Nov 2019
Number subjects received ≥1 vaccine	30	30	183	368	490	--
Timing of vaccination	May to Oct 2019	Apr to Sep 2019	Jun to Nov 2019			--
Number subjects AL dosed prior to Vax #3	29	--	181	--	--	--
Timing of AL dosing prior to Vax #3	Aug to Oct 2019	--	Aug to Nov 2019	--	--	--
Number subjects underwent DSF ≥1	--	26	--	358	--	--
Timing of start -end of DSFs	--	Sep to Dec 2019	--	Sep 2019 to Mar 2020	--	--

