### 9.1 Study Site

The study will be carried out in collaboration between the LMIV/National Institutes of Health (NIH) and the MRTC headquartered in Bamako, Mali. The study will be conducted by the MRTC at one location in Mali, West Africa (see [Figure 29](#)). The MRTC staffing at the Mali site is employed by NIAID/ University of Sciences, Techniques, & Technologies of Bamako (USTTB) programs and assigned to the Doneguebougou site for the duration of the study to provide clinical care and execute the protocol.

Doneguebougou is a community located 30 km north of Bamako and has a population of about 2,000 people, with another 2,000 inhabitants in the surrounding villages. For the purpose of vaccine trials and epidemiology studies, adequate facilities have been put in place at Doneguebougou within walking distance to the residents' homes. At Doneguebougou, malaria transmission is highly seasonal, with the transmission season taking place from June until December. Doneguebougou is situated in a high transmission area, with entomological inoculation rates (determined by human landing catch) as high as 137 to 167 infectious bites per person over one transmission season. There is a high study participation rate per compound in Doneguebougou, thus this site greatly fits the goal of a community-wide vaccination strategy such as what is being proposed for these TBV vaccines.

The additional nearby village to Doneguebougou, named Sirababougou, will also be approached for enrollment. Sirababougou is located at about 5km northeast of Doneguebougou village, the main site (see [Figure 29](#)). The population of Sirababougou is about 700 inhabitants based on the census performed at the beginning of this year by the study team. The population's primary occupation is mainly farming and the sociocultural behavior of the Sirababougou village is

[figure not shown]
similar to Doneguebougou. Malaria transmission intensity is expected to be similar to Doneguebougou village.

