## 17.2 Main Study

### 17.2.1 Primary Objective

To assess vaccine activity of Pfs230D1M-EPA/AS01 against *P. falciparum* transmission by direct skin feeding assay (DSF) (Arms 1a/1b and 3c/3d only)

A Poisson type model with compound level clustering with offset for the number of DSF tests that were performed will be used. The primary analysis of activity measured by DSF will be the Poisson GEE, which will be performed on the data once with Pm/Po midguts, and once without. The proportion of subjects infecting at least 1 mosquito in at least 1 DSF over the primary analysis period following dose 3 will be compared by use of a GEE model for binary response with compound level clustering.

Each of the above analyses will be performed on the subsample of subjects that had a concurrent positive BS (any parasite sexual and/or asexual) or rapid test positive with their DSF results.

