**Figure 32. Simulated power under assumptions of 0.4, 0.5, and 0.6 vaccine activity.**

These simulations would indicate that a second year of study is required in order to capture more of the seasonal infections, as the DSFs were monitored only from September – March. To guard against scenarios in which the VA falls in the lower ranges, we intend to combine the endpoints from Year 1 and Year 2 to achieve the needed power to distinguish vaccine activity. With additional follow up time, it appears feasible to have power for the all above scenarios.

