### 17.3.2.3 Analysis

The primary DSF analysis will use a GEE model with compound level clustering and the number of positive DSFs as outcome will be used for analysis with an offset for the number DSF tests. The primary parasitemia analysis will be analogous. The primary analysis population will follow the intention-to-treat principle. Additional analyses will explore the effects of different covariates such as time since start of the rainy season, SMC treatment, compound-level vaccine coverage, or proximity to a control compound on vaccine efficacy.

The primary safety and immunogenicity analyses will compare the rates of AEs or levels of antibody/activity between vaccinated and control individuals using standard statistical methods that respect compound-based randomization, as appropriate.

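### The primary skin-feed model treats every feed in two pooled years as equal exposure, which leaves the result needlessly dependent on each arm's mix of feeds

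*Combined protocol and SAP*

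**What the plan says.** The primary model is stated twice. Section 17.2.1: "A Poisson type model with compound level clustering with offset for the number of DSF tests that were performed will be used". Section 17.3.2.3: "The primary DSF analysis will use a GEE model with compound level clustering and the number of positive DSFs as outcome", again with the number of tests as offset. Neither statement has a term for season, calendar date or year. Section 17.3.2.3 goes on: "Additional analyses will explore the effects of different covariates such as time since start of the rainy season". That sentence lies outside the primary analysis, is worded for vaccine efficacy, and does not list study year among its examples.

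Section 12.6.4 times the feeds from each child's own dose: the first 14 days after it, then every 14 days, 8 in all after dose 3 and 10 after dose 4. Section 9.1 says "malaria transmission is highly seasonal, with the transmission season taking place from June until December". Table 7 gives the Year 1 feeding dates of the main-phase 9-18 year olds as "Sep 2019 to Mar 2020". The Protocol Summary places the fourth vaccination in June to October 2020, and Appendix A gives it a window of ±112 days.

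On pooling, the text below Figure 32 in Section 17.3.2.1 says "we intend to combine the endpoints from Year 1 and Year 2 to achieve the needed power", without saying how. The companion binary analysis in Section 17.2.1 is still defined over a period that starts at dose 3, with no stated length and no mention of dose 4.

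**The concern.** A count model with an offset for the number of feeds assumes that each feed carries the same baseline chance of a positive result. The protocol argues otherwise. Section 1.2.3.1 moved dose 3 forward so that antibody would be high when positive feeds are most frequent. In the adult trial (Table 6) the comparator rate differed 2.6-fold between two consecutive years.

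If the arms contribute different proportions of feeds from a high-rate and a low-rate year, or from in-season and out-of-season dates, the pooled rate ratio moves without any vaccine effect. If the proportions are equal, nothing is biased, but variation that could be explained stays in the error. The questions are how large each effect is and whether the design already protects against it.

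**Working it through.** **1. The plan's own figures.** Year 1 positivity is 70/2875 = 2.43% (Section 3.3.3), and 45/369 = 12.2% of children were positive (Section 17.3.2.1). Table 17 asks for 64 positive children at activity 0.5 and power 0.80. Schoenfeld's formula, 4(1.96 + 0.842)²/(ln 0.5)², gives 66, close to the stated 64. Activity 0.6 gives 38 (stated 40), and activity 0.4 gives 121 (stated 115). This reads the printed alpha of 0.5 and type 1 error rate of 0.8 as alpha 0.05 two-sided and power 0.80.

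**2. Calendar spread in Year 1.** Eight feeds 14 days apart span 98 days. With feeds on schedule, a series starting on 1 September 2019 ends on 8 December. A series ending on 1 March 2020 starts on 24 November: three feeds fall by the end of December and five after it.

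**3. Year contrast in the adult trial (Table 6).**

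| | 2017 | 2018 | Pooled |
|---|---|---|---|
| Comparator | 21/2462 = 0.85% | 55/2498 = 2.20% | 76/4960 = 1.53% |
| Full dose | 5/1231 = 0.41% | 5/1285 = 0.39% | 10/2516 = 0.40% |
| Activity | 52% | 82% | 74% |

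The comparator year ratio is 2.20/0.85 = 2.6 (2.58 from the unrounded rates). The pooled activity is a blend of two different yearly values, each resting on five vaccine-arm events.

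**4. What an unequal feed mix does with no vaccine effect.** Let R be the Year 2 to Year 1 rate ratio, and let w_v and w_c be the Year 2 shares of feeds in the vaccine and control arms. Then

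apparent activity = 1 − [1 + w_v(R − 1)] / [1 + w_c(R − 1)].

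- Equal shares (10/18 = 55.6% in both arms): 0%.
- Illustrative retention of 80% vaccine and 95% control: w_v = 8/16 = 50.0%, w_c = 9.5/17.5 = 54.3%. R = 2.59 gives 3.7%, R = 4 gives 4.9%, and R = 0.5 gives −2.9%.
- Shares of 50% and 60% at R = 2.58: 1 − 1.790/1.948 = 8%. Over R = 1.5 to 4 this case gives 4% to 11%.

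**5. Simulation.** Inputs: 100 units of 4 children (the size in Section 17.3.2.1) and 8 + 10 feeds. Assumptions: first feeds staggered over 75 days; a seasonal decline of 1-, 3- or 10-fold over 180 days; R = 1 or 2.59, with 0.5 and 4 also tried. There were 1,500 trials per scenario, with unit-clustered Poisson models. Model (a) has arm and the feed-count offset. Model (b) adds calendar day, its square and year.

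| Scenario | Model (a) | Model (b) |
|---|---|---|
| No effect, equal 90% retention: type I error | 0.053-0.071 | 0.051-0.073 |
| Same, 10-fold decline, R = 2.59: SD of log rate ratio | 0.247 | 0.239 |
| Activity 0.5, R = 2.59, 3-fold decline: power | 0.803 | 0.811 |
| Activity 0.5, R = 2.59, 10-fold decline: power | 0.748 | 0.775 |
| No effect, 80%/95% retention, R = 2.59 or 4: median activity | +2.9% to +4.7% | −0.3% to +0.4% |
| Same retention, R = 0.5: median activity | −2.0% | +0.7% |

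With equal retention and no effect, median activity lay between −1.7% and +1.4% over both models. The SD reduction is 1 − 0.239/0.247 = 3%. Each power figure has a simulation error of about √(0.8 × 0.2/1500) = 0.010, so the gain is small at best. At the 95th percentile, adjustment moves a single trial's log rate ratio by 0.06 (3-fold) or 0.11 (10-fold), that is, about a quarter to nearly half of an SD of 0.24.

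**The case against.** A reader might infer that season and year confound the vaccine effect, or that the primary test is invalid. The documents do not support that. Whole units are randomised, in similar numbers per arm (Section 17.4), blinded and followed concurrently, so calendar time is balanced in expectation. Start date is largely a feature of the unit, and the GEE clusters on compound, so chance imbalance is already reflected in the standard error. Step 5 agrees: both models are centred near zero with like type I error. This part of the objection stands in full.

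The case for unequal carry-over is also thin. In the adult trial, 82 of 116 vaccinees (71%) and 80 of 120 controls (67%) received the fourth dose. Year 2 shares of feeds were 2567/4966 = 51.7% and 2498/4960 = 50.4%. At R = 2.58 the formula in step 4 gives an apparent activity of about −1%, trivial and against the vaccine. A route to imbalance does exist: under Section 8.4 children aged 9-18 re-enter Year 2 only by receiving dose 4, Section 15.12 generally stops vaccination after a related Grade 3 event, and Section 12.6.4 lets children decline feeds. But only 3 of 398 children in that age group (0.8%, arms combined) had related Grade 3 events in Year 1 (Section 3.3.1.3).

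The seasonal gradient in children is uncertain as well. Section 4 reports 2% positivity in March against 2.5% or higher expected over the season. The adult year contrast comes from adults, fed for 12 weeks in one year and 16 in the other. These points limit the size of the concern. They do not give a reason to leave recorded dates out of the model.

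**Conclusion.** The point holds as a matter of efficiency and robustness, not of validity. The feed-count offset gives up as much as about 3% in standard error. It also leaves the result exposed to any difference between arms in Year 2 carry-over or missed feeds. In the illustrative 80%/95% retention case that exposure is about 3 to 5 activity points in the vaccine's favour when Year 2 is the higher year, and about 2 the other way when it is the lower.

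These sizes rest on assumed retention, stagger, seasonal gradient and year ratio; the documents contain no Year 2 retention or feed data. Year is the stronger argument and season within year the weaker. It might also be inferred that the blood smear model needs the same terms. No calculation here bears on that model, so nothing is claimed about it. Separately, the period starting at dose 3 in Section 17.2.1 and the two-year pooling in Section 17.3.2.1 do not agree, and a pooled figure alone could hide a difference in activity between years.

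**What to change.** Amend Sections 17.2.1 and 17.3.2.3 to one common statement, before unblinding:

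- Fit the primary DSF GEE on feed-level records with a fixed term for study year and a few broad calendar periods, for example in season versus after December. Keep the intention-to-treat set and vaccine-unit clustering. Child-by-year records with a feed-count offset and a year term are a simpler alternative that removes the dependence on year mix.
- Write the rule for merging sparse periods into the SAP, based on blinded totals of positive feeds.
- Report vaccine activity for each year beside the combined estimate.
- Define the primary analysis period once, stating whether it covers dose 3 only or both years, for the count and the binary analysis alike.

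The cost is SAP wording and a few extra parameters, with no new data, since each feed belongs to a scheduled visit. The downside is sparse events: Year 1 had 70 positive feeds in 45 children, so a full set of month terms would be too fine. With a log link and a constant rate ratio, these terms do not change what the arm coefficient means.

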Upon determining that Pfs230D1M-EPA/AS01 is safe in children 5-18 years of age, all eligible residents 5 years of age and older in identified participating family compounds/vaccine units will be enrolled for vaccine administration to assess safety and efficacy. Subjects will receive study vaccine or comparator vaccine according to the family compound assignment at 0, 28, and 56 days. Safety outcomes will be monitored and reported as local and systemic adverse events and serious adverse events (SAEs). Vaccine efficacy will be assessed by blood smear (BS) microscopy for detection of new *P. falciparum* infections in children 1-8 years of age living in the compound as well as 9-18 years of age. Vaccine activity will be assessed in children 9-18 years of age by DSF assays whereby laboratory-raised mosquitoes are fed on study participants' skin.

Our previous studies indicate that treatment with artemether-lumefantrine (AL) can reduce the rate of positive DSF assays for 4 or more weeks. For this reason, children 9-18 years of age who will undergo DSF to assess vaccine activity will not receive AL treatment before their 3rd or 4th vaccine dose. Since they are not receiving treatment before the transmission season, we will explore their reduced risk of infection as compared to controls on the basis of the proportion of positive BS.

We hope that the results of this study will help us determine the safety and tolerability of Pfs230D1M-EPA/AS01 in Malian children and to assess its functional activity as well as its efficacy to prevent *P. falciparum* infection.

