In 2013, LMIV employed DSFs in a vaccine study whereby gametocyte-positive vaccine participants were invited to undergo DSFs post third vaccination of a Pfs25 vaccine product (13-I-N109). In 2014, DSFs were expanded to cover all vaccine participants enrolled in the Pfs25 trial for a 6 week period post vaccination 4 to explore whether DSF assays could be used to measure functional activity endpoints.

Also in 2014, LMIV conducted a PfSPZ vaccine trial in Doneguebougou, Mali, and conducted DSF assays on all vaccine participants for 6 weeks post vaccination 4 to determine if the vaccine had an effect on interrupting malaria transmission (14-I-N159).

In 2015, LMIV initiated a second TBV trial using the combination of Pfs25 and Pfs230 antigens (15-I-0044). Vaccine enrollees were again invited to undergo DSFs twice weekly post vaccinations 3 and 4 for a 6-week period. This represented the largest number of DSFs conducted by the Mali-LMIV team to date with 2,005 conducted in 2015 and 1,844 conducted in 2016.

A Phase 1 trial of Pfs25M-EPA/AS01 combined with Pfs230D1M-EPA/AS01 in adults in Bancoumana and Doneguebougou enrolled in April 2017, and an important secondary objective of the trial will be to compare mosquito infectivity in vaccinated subjects versus the comparator group. To date 4,865 DSFs have been performed in this study.

[figure not shown]
Research at LMIV examining what factors lead to a positive DSF are ongoing, but the strongest correlate to a positive DSF is host gametocyte density: Individuals with a higher gametocyte prevalence in their peripheral BS are more likely to give a positive DSF. This, however, is not always the case and some individuals with high gametocyte burdens do fail to infect mosquitoes. A possible explanation may be recent ingestion of antimalarial drugs which are known to ablate transmission. Likewise, positive DSFs do occur from individuals who are BS-negative for gametocytes, indicating that sub-patent gametocyte levels are still able to infect mosquitoes in some cases.

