Gametocyte carriage varies with age, with younger age groups (<10 years old) having higher gametocyte carriage rates and densities. We have also been able to better understand the epidemiology of malaria transmission in this area. Based on data collected in the first 2 years (2011-2012) of our transmission-blocking assay study (11-I-N143), gametocyte carriage rates are higher in children 5-17 years old and in adults below the age of 35 years, compared to rates in children under 5 years. Mapping data has also identified housing clusters with higher carriage rates.

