### 17.4 Randomization

See [Section 11.2](#) for more information on individual study schedule.

This study will be cluster-randomized with family compounds, or groups of compounds (vaccine units) serving as the unit of comparison. A listing of the compounds in the study area with the numbers of individuals residing in their compounds will be created and used for randomization. The number of vaccine units will be the similar for each group. Enumerated compounds should have a target of approximately 80% participation rate of eligible participants for inclusion as a study unit, but consideration will be given to the number of children to finalize the decision for inclusion. Randomization for the full trial needs to be completed prior to the age de-escalation so that the randomization for vaccinated participants in the pilot phase study holds through the main phase.

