**Study Day -7 (±7 days; Drug Treatment Visit)**

1. Perform basic history and focused physical examination, emphasizing examination of any acute complaints.
1. Record vital signs (blood pressure, temperature, and heart rate).
2. Record AEs and concomitant medications, if applicable.
3. Obtain approximately 7.5 mL of blood for CBC with differential and platelet count, ALT, creatinine, hemoglobin typing, malaria blood smear and malaria PCR, and transcriptional analysis. (NOTE: if hemoglobin typing not obtained, can be obtained later during study at anytime when an EDTA tube is drawn). If safety labs were obtained for screening within  $\leq 2$  days prior to day -7, can use for study day -7 visit and do not need to repeat.
4. Obtain Urine +/- Stool Sample for Schistosomiasis +/- Helminth testing (permissible to be collected any day between start of AL dosing and first vaccination)
5. For females, obtain a urine or serum sample for  $\beta$ -hCG testing. Ensure that the test is negative before proceeding.
6. For females, ensure agreement and compliance with pregnancy prevention before AL dosing.
7. Administer first dose of artemether/lumefantrine (AL).
  - a. Additional doses of AL will occur on study days -6, -5

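### The primary DSF model could pre-specify age and the Day -7 blood smear as covariates; the unadjusted analysis is valid, and the likely gain in precision is modest

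*Combined protocol and SAP*

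**What the plan says.** Two sections define the primary DSF analysis. Section 17.2.1: "A Poisson type model with compound level clustering with offset for the number of DSF tests that were performed will be used". Section 17.3.2.3: "The primary DSF analysis will use a GEE model with compound level clustering and the number of positive DSFs as outcome", again with an offset for the number of feeds. Neither names a baseline covariate.

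Covariates appear only as further work in 17.3.2.3: "Additional analyses will explore the effects of different covariates such as time since start of the rainy season, SMC treatment, compound-level vaccine coverage". The list is open-ended and refers to vaccine efficacy; age and baseline infection are not among its examples.

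On allocation, Section 17.4 says: "The number of vaccine units will be the similar for each group". It also says that a listing of compounds with resident numbers is used for randomisation, without saying how. Age and infection are not mentioned as stratification factors.

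The candidate covariates are scheduled. For 9-18 year-olds the Day -7 visit in Appendix B reads: "Obtain approximately 7.5 mL of blood for CBC with differential and platelet count, ALT, creatinine, hemoglobin typing, malaria blood smear and malaria PCR". Section 12.5.1 has smears examined for asexual and sexual stages. The blood is taken before the first AL dose and a week before vaccination 1.

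On prognosis, Section 4 says that "the strongest correlate to a positive DSF is host gametocyte density", and that "Gametocyte carriage varies with age, with younger age groups (<10 years old) having higher gametocyte carriage rates and densities".

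**The concern.** Positive feeds are rare. Year 1 gave 70 positives in 2875 feeds, from 45 children (Sections 3.3.3 and 17.3.2.1). Section 17.3.2.1 says that this rate fell below what 0.8 power required, and the years are to be combined to recover it. With so few positive children, a chance difference between arms in age or prior infection can move the estimated vaccine activity (VA, one minus the rate ratio), and any outcome variation that these variables explain stays in the standard error. With a log link, adjusting for baseline covariates that are independent of arm leaves the rate ratio being estimated unchanged, so adjustment would not alter the question.

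Timing matters too. The text describes the study as still blinded. Covariates chosen after unblinding, once an imbalance has been seen, would be open to challenge; covariates fixed now would not.

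**Working it through.** **1. The plan's own event figures.** Table 17 asks for 64 positive children at VA 0.5 and 80% power. I take alpha as 0.05 two-sided (0.5 is printed). With 1:1 allocation, d = 4(1.960 + 0.842)² / [ln(1 - VA)]².
- VA 0.5: 4 × 7.849 / 0.4805 = 65.3, so 66 (stated 64).
- VA 0.6: 38 (stated 40).
- VA 0.4: 121 (stated 115), about 5% off.

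With 45 positive children and VA 0.5, the expected z is (√45 / 2) × 0.693 = 2.325, and power is Φ(2.325 - 1.960) = 0.64. Year 1 alone is short of 0.8, as the plan says.

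**2. How much one covariate can explain.** Inputs from the documents: 70/2875 = 2.43% positive per feed; intra-subject correlation ρ = 0.14; 8 feeds in Year 1, and 8 + 10 = 18 over both years. Prevalence q and rate ratio RR of a binary covariate are not in the documents; I assume q of 10-50% and RR of 1.5-5.

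- Total between-child variation (squared CV): 0.14 × 0.9757 / 0.0243 = 5.62.
- Part due to the covariate: c = q(1 - q)(RR - 1)² / [1 + q(RR - 1)]².
- Share: f = c / 5.62.
- Variance ratio, adjusted to unadjusted, with m feeds: [1 + (m - 1)ρ(1 - f)] / [1 + (m - 1)ρ].

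Example, q = 0.3, RR = 3: c = 0.84 / 2.56 = 0.328; f = 0.058. With m = 18: (1 + 2.38 × 0.942) / 3.38 = 0.959, a fall of about 4%.

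**3. Simulation, one covariate.** Beta-binomial feeds, 100 compounds of 4 children (the plan's power design), VA 0.5, Poisson GEE with compound-robust variance, 3000 trials per setting. Total ρ is held at 0.14, so the covariate takes a share of it. Results at q = 0.3:

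| Feeds | RR | Variance ratio | Power, unadjusted to adjusted |
|---|---|---|---|
| 8 | 1.5 | 0.999 | 0.565 to 0.568 |
| 8 | 2 | 0.989 | 0.566 to 0.566 |
| 8 | 3 | 0.971 | 0.565 to 0.576 |
| 8 | 5 | 0.932 | 0.554 to 0.594 |
| 18 | 1.5 | 0.997 | 0.678 to 0.678 |
| 18 | 2 | 0.981 | 0.687 to 0.701 |
| 18 | 3 | 0.963 | 0.686 to 0.706 |
| 18 | 5 | 0.932 | 0.681 to 0.724 |

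Rows should be read across, since a single power has a Monte Carlo error near √(0.57 × 0.43 / 3000) = 0.009. Over q of 10-50%, variance falls 0-2% at RR 1.5-2, 2-4% at RR 3 and 3-8% at RR 5. The power gain is at most about 1.5 points at RR 2 or less, and about 4 points at RR 5.

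**4. Two covariates together.** For independent predictors, 1 + c = (1 + c₁)(1 + c₂). With prevalences 40% and 30% and ratios 2 and 3: c₁ = 0.24 / 1.96 = 0.122; c₂ = 0.328; c = 1.122 × 1.328 - 1 = 0.491; f = 0.087. At 18 feeds the variance falls by 2.38 × 0.087 / 3.38 = 6%.

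Simulations with 384 children, 137 units, 18 feeds and VA 0.45, over several assumed prevalences, agree:

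| Ratios | Variance falls | Power gain, points |
|---|---|---|
| 1.5 and 2 | 0-2% | 0.3-1.2 |
| 2 and 3 | 5-8% | 0.4-3.5 |
| 3 and 4 | 8-16% | 2-8 |

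Type I error was unchanged by adjustment (0.052 against 0.053; 0.061 against 0.063) and mean estimates agreed within 0.005. At ratios 2 and 3, the adjusted and unadjusted VA differed by about 0.07-0.08 or more in one trial in ten.

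**5. Cross-check.** Power 0.69 corresponds to an expected z of 1.960 + 0.496 = 2.456. An 8% fall in variance raises it to 2.456 / √0.92 = 2.561, and power to Φ(0.601) = 0.726, a gain of 3.6 points.

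**The case against.** The best case for leaving the model alone is that an unadjusted intention-to-treat comparison in a randomised trial needs no repair, and that the documents do not show these covariates to be strong. Both parts stand, and they limit the point in several ways.

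A reader might infer that the protocol itself ties pre-vaccination infection to later infectiousness. It does not: Section 4 links a positive feed to gametocyte density, not to infection before vaccination. All these children receive AL from Day -7, and Section 1.2.3 notes that "treatment with artemether-lumefantrine (AL) can reduce the rate of positive DSF assays for 4 or more weeks". The first main-phase feed is nominally Day 70, 77 days or 11 weeks after the smear; Year 2 feeds come more than a year after it. The smear may still mark local exposure, since Section 1.2.2 describes household clusters lasting several months, but that is inference.

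A reader might infer a steep age effect. Section 4 separates those under 10 from older people, so only 9-year-olds in the analysed band fall on the younger side, and no gradient within 9-18 is given.

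A reader might infer that randomisation left the arms unbalanced. The text shows only that these factors are not described as stratification factors. Allocating about 137 units at random balances them in expectation, so there is no bias.

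A reader might want village and PCR in the model, or the same change for smears in 1-8 year-olds. Section 9.1 expects similar transmission in both villages, Section 12.5.3 says only that qPCR may be done, and no calculation here supports the change for younger children.

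Finally, the open covariate list and the analysis of children with a concurrent positive smear or rapid test might seem to cover the matter. They do not supply a pre-specified, baseline-adjusted primary estimate, and the second selects on status after vaccination.

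**Conclusion.** The point holds in a limited form. The primary DSF model uses no baseline information, although two suitable variables are scheduled before treatment and adjustment leaves the rate ratio unchanged. The unadjusted result would be valid. Under assumed rate ratios of 1.5-3, variance falls by about 0-8% and power rises by about 0-4 points; gains beyond that need ratios that nothing in the documents supports, and weak predictors would gain almost nothing. These figures rest on 2.43% positivity per feed, a total intra-subject correlation of 0.14, assumed prevalences, and VA of 0.45-0.5. This is an inexpensive improvement for a trial short of events, not a defect that threatens its conclusion.

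**What to change.** In Sections 17.2.1 and 17.3.2.3, before unblinding, state that the primary DSF GEE contains arm, age at enrolment (continuous) and Day -7 blood smear status (positive if asexual parasites and/or gametocytes are seen), with the same log link, feed offset and compound clustering. Keep the unadjusted model as a named sensitivity analysis. Give children without a Day -7 smear their own category. Leave village out, and leave PCR out unless it is confirmed as done for every child.

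The cost is a sentence or two in the plan and trivial programming. The downside is small: the missing-smear category adds a term, and the gain may be negligible if the predictors prove weak.
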